Protocol for Proposed Pilot Study: Family-Authored ICU Diaries to Reduce Fear in Patients Experiencing a Cardiac Arrest (FAID Fear)

NCT Number: NCT05144477

Document Date: 7/5/2022

1. Study Purpose and Rationale

A cardiac arrest (CA) is a terrifying experience for patients, but maybe even more so for their loved ones. Whereas patients are not conscious and often have little to no memory of the CA and associated stay in the hospital and the intensive care unit (ICU),^{1,2} families witness all of these things, resulting in high levels of fear and psychological distress. Indeed, ~1/3 of family members of ICU patients report clinically significant posttraumatic stress symptoms (PTSS).³ This phenomenon is so prevalent that it has been termed Post-Intensive Care Syndrome – Family (PICS – Family).³⁻⁵

Critically, emotions are socially transmitted,⁶⁻⁸ memories are socially constructed,⁹⁻¹³ and partner distress can undermine the provision of skilled social support that can buffer patient distress.^{14,15} Prior research has suggested that patients experiencing CA will develop memories of the CA event over time^{1,2} – potentially because they are trying to “fill in the gaps” in their memory.¹⁶ As such, **partners or other close family members may play a critical role in creating and cementing fear-based memories and distress in patients experiencing a CA.** CA patients often report cardiac fear and preoccupation.¹⁷ This is not without consequence: fear-based distress, particularly early anxiety related to symptoms (e.g., rapid heartbeat) and markers for PTSS in other patient populations predicts reduced engagement in behavior necessary for secondary prevention (e.g., reduced physical activity, medication avoidance) and increased morbidity and mortality.¹⁸⁻²⁴

The present study will test the feasibility of a Family-Authored ICU-diary intervention to reduce fear of CA in patients’ partners/family members, with the long-term goal of developing and implementing a large scale RCT to test whether fear reductions in family members improve patients’ mental wellbeing, health behaviors, and, ultimately, health outcomes. Following the methods of a RCT published in 2020,^{25,26} partners/family members will receive a bound diary from a trained research assistant and a brief explanation of how to use the diary, including recommended frequency for writing and tips on how to express themselves. This intervention found that family-authored diaries significantly reduced PTSS in family members (26.3% lower in intervention v. control conditions, 95% CI 4.8, 52.2) and trended towards a reduction in PTSS for patients (11.2% lower, 95% CI -15.7, 46.8).^{25,26}

Aim 1: Enroll 31 partners/family members of CA patients to **(a)** pilot recruitment procedures, **(b)** estimate retention, and **(c)** assess acceptability of study procedures.

Partners/family members will be randomized to either complete an ICU diary^{25,26} or to a control condition, and will complete surveys in the ICU or hospital floor, at patient end of hospital care (contingent upon discharge status), and 30 days post-end of hospital care.

Aim 2: Obtain an estimate of the association of intervention v. control with **(i)** partner/family member fear (operationalized as cardiac anxiety *about the patients’ cardiac condition*) at hospital discharge and **(ii)** partner/family member PTSS 30 days post-discharge.

Exploratory Aims: Obtain an estimate of the association of intervention v. control with partner/family member aversive cognitions towards exercise at hospital discharge.

2. Study Design and Statistical Analysis

This is a randomized control study design using an intervention v. control condition. It is a pilot feasibility trial of up to 31 participants.

Participants will be drawn from caregiver participants enrolled in the CANOE study (AAAR8497), who have indicated they are willing to hear about additional research opportunities and who meet initial study criteria.

Eligibility

- 1) the primary partner or family member of a patient who has experienced a cardiac arrest,
- 2) age 18 years and over,
- 3) able to speak, read, and write in English or Spanish,
- 4) participating in the CANOE study and indicated they were willing to hear about future research opportunities,
- 5) willing to write in a journal about their experiences,
- 6) available for follow-up, and
- 7) does not have any medical or psychiatric impairment that would prevent them from complying with the research protocol.

Sample size and power estimates are based on Aim 1. Although some have used pilot studies to estimate effect sizes on primary outcomes, we agree with leaders in our field who argue that effect size estimates from small pilot studies are too imprecise to meaningfully inform effect size assumptions of power analyses for larger, later stage studies. Therefore, we do not provide power calculations for the effects of our intervention on fear-based mechanisms or behavioral outcomes. We will, however, use estimates from these studies (e.g., standard deviations, attrition rates) to help determine appropriate sample sizes for a subsequent study that is powered to detect meaningful reductions in measures of cardiac anxiety.

As this is a pilot study, our sample size was guided by the need to enroll enough participants – specifically, family members or partners of patients who recently survived CA – to examine the feasibility of conducting a larger stage II or III randomized clinical trial of our FAID-Fear intervention in this population. In particular, we will determine whether we are capable of recruiting, retaining, and assessing participants, and of implementing the proposed intervention with good compliance.

3. Study Procedures

IRB-approved personnel from the CANOE (AAAR8497) research team will identify participants enrolled in the CANOE study as part of the caregiver cohort who have indicated they are willing to hear about additional research opportunities and who meet initial study criteria. Members of the CANOE research team will generate a list that includes the CANOE caregiver participant

name, CANOE patient participant MRN, patient location, caregiver relationship to the patient, and caregiver contact information. The list will be sent to a member of the FAID Fear study team via encrypted email. Using the list, the FAID Fear study coordinator will either approach potentially eligible partners/family members in the ICU/hospital or contact them via telephone. A verbal information sheet that explains overall study participation will be used to complete the consent process.

Partners/family members who undergo informed consent and agree to participate will be randomized 2:1 to either the ICU diary (intervention) or the control condition. Randomization will occur using opaque sealed envelopes to be opened by the study coordinator after consent is provided/document. The partner/family member participant will be informed of the randomization assignment and a baseline assessment will also occur.

Randomized to ICU Diary Condition

These partners/family members will receive standard contact and communication from ICU/hospital doctors.

Following the design of Nielsen et al.,²⁵ partners/family members will be provided with a hard-cover diary containing written instructions (diary instructions included in RASCAL attachments) and a pen. If consent and randomization occur in person, the diary will be handed to the participant. If consent and randomization occur by phone, the diary will either be mailed to the participant or the coordinator will arrange for a time to meet the participant in the hospital or at the CBCH offices to provide the diary. A trained research assistant will explain how to use the diary, and instructions will include recommended frequency for writing and tips on how to express themselves. The hard copy of the diary will remain with the partner/family member participant and they will be asked to continue writing in the diary until patient end of hospital care (e.g. ICU). The diary will not be collected at the conclusion of the study. Research assistants will check in with participants via weekly telephone calls to provide support, as needed, if the partner/family member reports difficulty in writing diary entries (e.g., suggesting the partner/family member write at home rather than in the hospital, encouraging use of key words or focusing on the present if events are hard to summarize).

We confirm that the hard-copy diary that is provided to subjects will not reference any identifiers or codes and the diary will NOT be collected back from participants as part of the study (once the blank diary is given to the participant, it is theirs to keep).

Randomized to Control Condition

These partners/family members will receive standard contact and communication from ICU/hospital doctors.

The CANOE patient MRN will be used to access the patient EHR to view/document the date of discharge or death. All FAID Fear study participants (both intervention and control) will complete 1) a survey upon end of hospital care (contingent upon discharge status; specifically, if a patient dies, then we will not contact family members at this time but will wait to contact them until one month has passed in accordance with the procedures of the CANOE-F team in

order to be respectful of, and sensitive to, the needs of participants for space and time), and 2) a final survey at 30 days post-end of hospital care (participants randomized to the control condition will not be asked questions about intervention appropriateness, feasibility, and acceptability, but will be asked if they kept a diary. If yes, they will be asked questions about diary usage). Upon completion of the 30-day survey, study participation is complete.

For analysis purposes, the data collected as part of this study will be shared with CANOE study (AAAR8497) researchers. The patient MRN number will be used to link partner/family member participant data from this study with data from the CANOE study.

In addition, identifiable data from the PACE study (AAAT4053) will be accessed and used as part of our analysis.

Compensation: Participants will be provided with compensation to acknowledge the time and effort put into study participation as follows:

- Payment for randomization - \$25.
- Payment for survey completion at baseline - \$25
- Payment for survey completion at 30-days post-end of hospital care - \$50

Total compensation for the completion of all study activity is \$100. Payments will be distributed in the form of Bank of America PayCards.

4. Risks

Study procedures (i.e., completing questionnaires and, as applicable, writing in an ICU diary) present minimal risk. The questions asked and the thoughts evoked during the course of this research study pose minimal risk of psychological discomfort, and participants may wish to skip any question or questionnaire that they choose. Participants will be made aware of these risks and will be assured they can terminate their participation in the study at any time without penalty. A mental health referral plan is outlined in the Data Safety and Monitoring section of this protocol.

Study participation also involves the possibility of a loss of confidentiality. The study team has outlined plans to protect participant confidentiality in the Privacy and Data Security section of RASCAL.

5. Benefits

There is no direct benefit to subjects who participate in this study. Results may be used to design future adequately powered RCTs to refine and develop ICU-based diary interventions. The information obtained as a result of this study may thus help future family members cope with the distressing experience of a loved one experiencing a cardiac arrest, and surviving patients may also benefit.

6. Alternatives

The alternative is not to participate.

7. Data and Safety Monitoring

As this study presents minimal risk to participants, data and safety monitoring will be conducted by the study staff as directed by the principal investigator. Thus, there is no plan for a Data Safety and Monitoring Board (DSMB).

Mental Health Referral Plan: To support subject well-being, all subjects will be asked if they would like to be provided with a mental health resource sheet (which reflects referral to General Psychiatry at Columbia University Irving Medical Center) at the 30-day contact.

If a participant expresses immediate risk of self-harm during study participation, we will follow mandated reporting requirements, which may include emergency room evaluation and/or psychiatric services. These safety procedures will be overseen by [name], who also holds a master's degree in Clinical Social Work, and has previous experience with counseling, care coordination, patient referrals, and client services.

Study Team Meetings: Investigators and research assistants will meet weekly to discuss any issues or concerns with the study, in particular, whether there were any unexpected complaints about the study procedures or questionnaires, or whether there were any breaches in data confidentiality (which will be reported to the IRB as required by policy). If unexpected complaints about the study tasks or questionnaires are generated, then the study may be stopped or altered prior to recruiting the full sample.

References

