Statistical Design and Power for Proposed Pilot Study: Family-Authored ICU Diaries to Reduce Fear in Patients Experiencing a Cardiac Arrest (FAID Fear)

NCT Number: NCT05144477

Document Date: 2/26/2021

Statistical Design and Power for Proposed Pilot Study: Family-Authored ICU Diaries to Reduce Fear in Patients Experiencing a Cardiac Arrest (FAID Fear): A Pilot Intervention Study

Aim 1: Enroll 15 partners of cardiac arrest (CA) patients and surviving patients to (a) pilot recruitment procedures, (b) estimate retention, and (c) assess acceptability of study procedures for both family members and patients in the intervention condition.

Aim 1 will be tested by assessing the following measures:

OUTCOME MEASURES

- 1) Proportion of eligible *partners* of cardiac arrest (CA) patients whom we approach who enroll in the pilot study.
- 2) Proportion of enrolled *partners* who complete the pilot study outcome assessments one month following either the death of the patient or patient discharge from the ICU.
- 3) Proportion of *partners* that adhere to the diary intervention (complete ≥ 2 diary entries/week).
- 4) Proportion of *partners* that agree that the intervention was acceptable using the mean of the 4-item Acceptability of Intervention Measure (score ≥ 4 ; 1 = *completely disagree*, 5 = *completely agree*).
- 5) Proportion of *partners* that agree that the intervention was feasible using the mean of the 4-item Intervention Feasibility Measure (score ≥ 4 ; 1 = *completely disagree*, 5 = *completely agree*).
- 6) Proportion of *partners* that agree that the intervention was appropriate for reducing cardiac anxiety about the patient's heart using the mean of the 4-item Intervention Appropriateness Measure (score ≥ 4 ; 1 = *completely disagree*, 5 = *completely agree*).
- 7) Proportion of eligible CA *patients* whom we approach who ultimately agree to participate in the pilot study.
- 8) Proportion of enrolled CA *patients* who complete the outcome assessments one month following discharge from the ICU.

Statistical approach for Aim 1. We will compute the proportions listed above, including 95% confidence intervals.

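### With phone consent the diary can arrive with little or no writing time left, and the pilot has no planned way to tell late delivery from non-adherence

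*Protocol*

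**What the plan says.** **Contact and randomization.** Under Protocol section 3 (Study Procedures), the coordinator "will either approach potentially eligible partners/family members in the ICU/hospital or contact them via telephone". Allocation, 2:1 in favour of the diary, uses "opaque sealed envelopes to be opened by the study coordinator after consent is provided/document".

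**Delivery.** In-person participants are handed the diary. After phone consent and randomization, "the diary will either be mailed to the participant or the coordinator will arrange for a time to meet the participant in the hospital"; the study offices are another option. No time limit is given.

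**Writing period.** Of diary-arm participants the Protocol says: "they will be asked to continue writing in the diary until patient end of hospital care (e.g. ICU". The diary stays with the participant and is not collected.

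**Eligibility.** Protocol section 2 lists seven criteria. The only one about the patient is that the caregiver is "the primary partner or family member of a patient who has experienced a cardiac arrest". None mentions current inpatient status, expected remaining stay or possession of the diary.

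**Measures.** SAP Aim 1, measure 3 is the proportion of partners "that adhere to the diary intervention (complete ≥ 2 diary entries/week". The SAP classes all partner measures under that aim as primary. Protocol Aim 2 estimates caregiver fear "at hospital discharge and (ii) partner/family member PTSS 30 days post-discharge".

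**The concern.** The writing window opens when the diary is received and closes at the patient's end of hospital care. Its opening waits on enrolment in the parent study, transfer of the contact list, contact, consent and the envelope. For phone consents, it also waits on mailing or a later meeting. Nothing in the plan keeps the opening ahead of the closing.

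One stated purpose of the pilot is to learn whether the intervention can be implemented with adequate compliance, and measure 3 is the figure that answers this. A low value could mean that caregivers will not write, or that the diary reached them too late. The first calls for a different intervention or more support, the second for different logistics. Without a receipt date, a larger trial would be planned without knowing which problem it faces. Because the diaries are not collected, dated entries cannot be consulted afterwards.

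**Working it through.** **Plan's own figures.** The documents give no share of phone consents, mailing time, length of stay or expected adherence, so there is no stated figure on this point to reproduce. The SAP's related precision figure does reproduce: for 90% retention with N = 15, 0.90 ± 1.96 × √(0.90 × 0.10 / 15) = 0.748 to 1.052, which truncates to the printed 75% to 100%. It is not in dispute.

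**Step 1: can the window be empty?** For a phone consent the order is consent, envelope, dispatch, receipt. The window closes at an event outside the study's control. With no rule linking receipt to that event, the window may be short or empty even when the patient was in hospital at randomization.

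**Step 2: what does measure 3 return then?** Let E be the number of entries and D the days from receipt to end of hospital care. The weekly rate is E / (D/7) = 7E/D.
- If D = 0, the rate is undefined.
- If E = 1, the rate is 7/D, which is at least 2 whenever D ≤ 3.5. One entry then counts as adherent if the rate is prorated, but not if two actual entries in a week are required. The SAP does not say which.
- If time is counted from randomization instead of receipt, days without a diary count against the participant.

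**Step 3: weight of each affected person.** Inputs are up to 31 participants and 2:1 allocation (Protocol). The diary arm is 31 × 2/3 = 20.7, about 21, so each person is 1/21 = 4.8 percentage points. (If the same ratio applied to the SAP's N = 15, the arm would be 10 and each person 10 points.)

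The number affected, m, is an assumption shown as a range. If 80% of the others adhere (also assumed), the expected proportion over the whole arm is 0.80 × (21 − m)/21:

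| m of 21 | Highest attainable adherence, (21 − m)/21 | Expected adherence, whole arm |
|---|---|---|
| 0 | 100% | 80.0% |
| 2 | 90.5% | 72.4% |
| 4 | 81.0% | 64.8% |
| 6 | 71.4% | 57.1% |

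For scale, the 95% half-width at 80% with n = 21 is 1.96 × √(0.80 × 0.20 / 21) = 17 points. Four late diaries would move the result by 80.0 − 64.8 = 15.2 points, nearly as much, and the planned data could not show why.

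**Step 4: the discharge contrast.** If a diary that arrives too late has no effect, m survivors' caregivers among 21 shrink the mean difference by m/21. For an assumed true effect of 0.5 SD, m = 2, 4 or 6 moves it by 0.05, 0.10 or 0.14 SD. The standard error with 21 against 10 is √(1/21 + 1/10) = 0.38 SD before dropout. The shift is well inside the noise.

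**The case against.** **Enrolment after discharge looks unintended.** A reader might infer from the silent criteria that caregivers of patients already at home would be randomized. The documents do not support that as the plan. The text under Protocol Aim 1 places the first survey in the ICU or on the hospital floor, the recruitment list carries the patient's location, and both arms are described as in contact with hospital doctors. This largely stands. These are descriptions, not an eligibility rule, and they do nothing about slow delivery to someone whose patient was in hospital at randomization.

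**Other safeguards.** A phone consent may lead to a hand-over in hospital, and the weekly calls might bring non-receipt to light. But the calls are described as support for difficulty in writing, and recording receipt is not mentioned.

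**A pilot should expose delivery failure.** Adherence over everyone allocated to the diary is a fair measure of the intervention as delivered. That stands. The complaint is only that non-delivery and non-writing are not reported apart.

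**Harm to Aim 2.** A reader might infer that the discharge difference is seriously diluted and that the next trial, planned on the estimate minus 1 standard error, would be inflated by a calculable factor. The documents do not support this. The affected fraction is unknown. If the patient dies, the family is not contacted at that point (Protocol section 3), so those caregivers affect adherence but have no discharge survey to dilute. The all-randomized contrast is a legitimate intention-to-treat estimate, and its standard error exceeds any plausible shift.

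**Conclusion.** The point holds as a gap in measurement. The plan permits a diary to arrive at or after the end of the requested writing period. It does not record receipt, so far as the documents show, and it scores adherence with a weekly rate that has no start, no window and no rule for short exposure. A primary feasibility measure therefore cannot separate late delivery from unwillingness to write, and the diaries will not be available to settle it.

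The size is about 4.8 percentage points of adherence per affected person, assuming a diary arm of about 21. The number affected is unknown, and the 2, 4 and 6 used above are illustrations. A reader might take the finding to be that the measures do contain people who had no chance to write. The documents show only that this can happen, and nothing forbids writing after the requested period. Dilution of the discharge contrast is a secondary matter, limited to caregivers of surviving patients. The change is worth making because it is cheap and the information is hard to recover later.

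**What to change.** 1. State as an eligibility criterion that the patient is still in hospital, checked in the health record just before the envelope is opened. It then applies to both arms and preserves randomization.
2. Record the date of diary receipt. Compute the writing window from it and the discharge or death date, which the Protocol already plans to take from the health record. Reconcile the event that closes the window: the Protocol gives the ICU as an example of hospital care but times Aim 2 by hospital discharge.
3. Report the proportion of the diary arm who received the diary before end of hospital care as a separate feasibility outcome.
4. Define measure 3 as participant-reported entries per week from receipt to end of hospital care, with a rule for windows under one week fixed in advance. Report it in all diary-arm participants, counting no receipt in the window as not adherent, and in those who received the diary in the window.
5. Keep the all-randomized comparison for Aim 2. A comparison limited to those who received the diary in time has no matching control subset.

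Two tempting additions should be left out. Holding the envelope until delivery before discharge is assured would need knowledge of a future discharge date. A fixed minimum number of days with the diary has no basis in the documents and would favour long stays.

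The cost is one extra data field and some wording in both documents. A few caregivers of patients already discharged would not be randomized. The inpatient check does not prevent slow mail, but items 2 to 4 make its effect visible.

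### As stated, the mental health resource sheet is offered only at the final 30-day contact; offering it at consent or baseline in both arms is a cheap, minor safety improvement

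*Protocol*

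**What the plan says.** Protocol Section 4 (Risks) sends the reader to a single place: "A mental health referral plan is outlined in the Data Safety and Monitoring section of this protocol". The plan in Section 7 has two steps.

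- **Resource sheet.** "all subjects will be asked if they would like to be provided with a mental health resource sheet". The sheet reflects referral to "General Psychiatry at Columbia University Irving Medical Center) at the 30-day contact".
- **Emergency route.** "If a participant expresses immediate risk of self-harm during study participation, we will follow mandated reporting requirements". The person overseeing these procedures has "previous experience with counseling, care coordination, patient referrals, and client services".

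Section 3 (Study Procedures) fixes where the 30-day contact falls. Participants complete "a survey upon end of hospital care (contingent upon discharge status; specifically, if a patient dies, then we will not contact family members" at that time; in that case contact waits until a month has passed. All participants then complete "a final survey at 30 days post-end of hospital care". After that, "Upon completion of the 30-day survey, study participation is complete".

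Section 3 also describes earlier contacts: consent, randomization and a baseline assessment in both arms, and weekly telephone calls in the diary arm only. The calls are described as help for participants who find the entries hard to write. No offer of the sheet is stated at any of these.

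**The concern.** Section 7 gives participant well-being as the reason for the sheet, and Section 1 describes families of cardiac arrest patients as highly fearful and distressed. Yet the written plan makes the offer only as participation ends, although staff are in touch with every participant from the day of consent.

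Two groups are served least well. Section 4 lets participants stop at any time, so those who leave early may never reach the one contact at which the sheet is offered. Bereaved participants lose the end-of-care survey, so after the death they hear nothing from the study for a month. A participant in either arm who is distressed, but not at immediate risk of self-harm, has no stated route to the sheet in the meantime.

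What is at stake is the timing of a modest support measure. No sample size, error rate or endpoint definition depends on it.

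**Working it through.** The plan gives no figure to reproduce. The check sets the scheduled contacts (Protocol Section 3) beside the referral plan (Protocol Section 7).

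| Contact | Who has it | Offer of the sheet stated? |
|---|---|---|
| Consent, randomization, baseline assessment | Both arms | No |
| Weekly calls | Diary arm only | No; purpose is help with writing |
| End-of-care survey | Both arms, only if the patient survives | No |
| 30-day survey (final) | Both arms | Yes |

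**Scheduled survey contacts without a stated offer**

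- Patient survives: baseline, end of care, 30 days = 3 contacts, offer at 1, so 3 − 1 = 2 of 3 without.
- Patient dies: baseline, one-month contact = 2 contacts, offer at 1, so 2 − 1 = 1 of 2 without.

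**Time from consent to first offer**

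The 30-day clock starts at the end of hospital care, not at enrolment. If L is the hospital stay remaining at consent, the first offer comes at about L + 30 days. With L = 0 this is 30 days, the minimum. The documents do not give L. As illustration only, an assumed L of 7 days gives 7 + 30 = 37 days, and an assumed L of 28 days gives 28 + 30 = 58 days.

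**Participants who might never be offered the sheet**

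The documents do not give this number. As illustration only, the SAP's expected retention of about 90% would imply 31 × (1 − 0.90) = 3.1, or about 3 of 31. That needs two conditions. The 90%, stated for N = 15, must carry over to N = 31. Failing to complete the assessment must also mean no contact at all. The second is doubtful: the SAP's retention measure counts completed assessments, whereas Section 7 ties the offer to the contact, so someone who is reached but declines the survey could still be offered the sheet.

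**Other protections in the documents**

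- Participants may skip questions or stop (Section 4).
- An overseer has counseling and referral experience (Section 7).
- Weekly team meetings cover complaints and confidentiality breaches, and can lead to stopping or altering the study (Section 7).
- The SAP allows an unblinded interim analysis and early stopping if adverse-event concerns arise (Planned Interim Analyses).

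These are real protections, but none is a stated earlier referral step for an individual participant.

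**After the change proposed below**

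Survey contacts with a scheduled offer go from 1 of 3 to 2 of 3 if the patient survives, and from 1 of 2 to 2 of 2 if the patient dies. The wait from consent to first offer goes from L + 30 days to none, or to delivery time where consent is by telephone.

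**The case against.** The strongest reply is that this is a preference about timing. The study is rated minimal risk, the sheet goes to every participant in both arms, an emergency route applies throughout participation, and no requirement is shown to be breached. This stands as to severity: the point is an improvement, not a defect.

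Second, the step may exist where we cannot see it. Consent pages were removed from the supplied files, and Section 3 refers to a verbal information sheet and to RASCAL attachments. Every participant is also a CANOE caregiver, and the pause after a death follows that study team's procedures. This stands in full, so the point is limited to what the supplied documents state.

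Third, the timing has some logic. Posttraumatic stress symptoms are a 30-day outcome, so the offer coincides with their measurement, whereas an earlier offer would precede it and could lower the scores. The documents do not give this rationale, but the effect is possible and belongs among the costs.

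Fourth, offers prompted by distress would arise more often in the diary arm, because only that arm has weekly calls. A reader might infer that this does not matter because the SAP says the pilot is not powered for the comparison. The documents do not support that. Low power does not remove bias, and the SAP's Aim 2 approach uses the mean difference less one standard error to size the larger trial. Any imbalance is probably small, but it should be recorded rather than excused.

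**Conclusion.** The point holds as a minor safety improvement. As stated in the supplied documents, the sheet is offered only at the final contact, and before then the only stated referral trigger is immediate self-harm risk. Participants who withdraw early may never be offered it, and bereaved participants are not contacted for a month.

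The size that follows from the documents is two of three scheduled survey contacts without an offer (one of two after a death), and a wait from consent of at least about 30 days. The longer waits and the count of about 3 of 31 in the working are illustrative and carry no weight in this conclusion. The conclusion assumes that the consent, RASCAL and CANOE materials do not already provide an earlier offer.

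Three stronger readings should be resisted.

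- A reader might infer that participants have no protection before day 30. The emergency route and the other protections listed above say otherwise.
- A reader might infer that the minimal-risk rating, or the absence of a monitoring board, is wrong. Nothing here bears on either.
- A reader might take the rate of about one third in Section 1 as the share of participants harmed by the late offer. That rate describes symptoms among families of ICU patients in general. It is not an effect of this study, and Section 1 does not say when the symptoms arise.

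**What to change.** Amend the Mental Health Referral Plan in Protocol Section 7 as follows.

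1. Offer the existing sheet to every participant, in the same words in both arms, at consent or baseline. Doing so at consent, before the randomization envelope is opened, ensures that the offer cannot differ by arm.
2. Keep the 30-day offer.
3. Give the sheet to any participant in either arm who asks for it or reports distress at any contact.
4. Record by arm who received the sheet, and when, because weekly calls exist only in the diary arm.
5. Leave the one-month pause after a death unchanged; the consent or baseline offer will already have been made.

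If consent, RASCAL or CANOE materials already provide an earlier offer, one sentence in Section 7 saying so is enough.

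The cost is a short wording change, an IRB amendment and one extra item to record. The sheet and the contacts already exist; for telephone consent the sheet would have to be sent. The scientific cost is a small co-intervention common to both arms. It may slightly lower 30-day posttraumatic stress scores and so slightly shift the estimates carried into the larger trial. The record of use by arm lets the team report any imbalance when those estimates are used.
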